Appendix C.: Liver Chemistry Stopping and Follow Up Criteria

Liver chemistry stopping criteria

Liver chemistry stopping and increased monitoring criteria have been designed to assure subject safety and evaluate liver event etiology (in alignment with the FDA premarketing clinical liver safety guidance). These criteria have been amended for this myositis protocol to accommodate for a specific population of myositis patients with ALT/AST abnormalities as a result of muscle injury. Baseline bilirubin, GGT and INR must be at or near normal. (Note: ULN – upper limit of normal as determined by the reference range of the local lab. All liver toxicities must be reported to the Sponsor (Northwell Health). Subjects that meet liver stopping criteria MUST be reported to GSK within 24 hours.)

- ALT Absolute:
 - ALT \geq 8xULN (without elevated CPK, and/or myoglobin)
 - If ALT \geq 8xULN **and serum GGT \geq 3xULN** (irrespective of CPK and/or myoglobin values)
- ALT Increase:
 - ALT \geq 5xULN but $<$ 8xULN (without elevated CPK, and/or myoglobin) **and GGT \geq 3xULN**, persists for \geq 2 weeks
 - ALT \geq 3xULN but $<$ 5xULN (without elevated CPK, and/or myoglobin) **and GGT \geq 3xULN**, persists for \geq 4 weeks
- Bilirubin: ALT \geq 3xULN and bilirubin \geq 2xULN ($>$ 35% direct bilirubin) ^{a, b}
- INR: ALT \geq 3xULN and INR $>$ 1.5, if INR measured ^b
- Cannot Monitor:
 - ALT \geq 5xULN but $<$ 8xULN (without elevated CPK, and/or myoglobin) **and GGT \geq 3xULN** and labs cannot be monitored weekly for \geq 2 weeks
 - ALT \geq 3xULN but $<$ 5xULN (without elevated CPK, and/or myoglobin) **and GGT \geq 3xULN** and labs cannot be monitored weekly for \geq 4 weeks
- Symptomatic: ALT \geq 3xULN (without elevated CPK, and/or myoglobin) **and GGT \geq 3xULN** associated with symptoms (new or worsening) believed to be related to liver injury or hypersensitivity ^c
 - a) Serum bilirubin fractionation should be performed if testing is available. If serum bilirubin fractionation is not immediately available, discontinue study treatment for that subject if bilirubin \geq 2xULN. Additionally, if serum bilirubin fractionation testing is unavailable, **record presence of detectable urinary bilirubin on dipstick**, indicating direct bilirubin elevations and suggesting liver injury.
 - b) All events of ALT \geq 3xULN (without elevated CPK, and/or myoglobin) **and GGT \geq 3xULN**

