- Liver imaging (ultrasound, magnetic resonance, or computerised tomography) and /or liver biopsy to evaluate liver disease: complete Liver Imaging and/or Liver Biopsy CRF forms.

Increased monitoring criteria with continued therapy

Criteria

- For subjects who have had IVIG in the past, additional HBVDNA testing must be completed when ALT or AST elevations increase to $>2.5\times\text{ULN}$ during the study
- If ALT $\geq 5\times\text{ULN}$ and $<8\times\text{ULN}$ (without elevated CPK, and/or myoglobin) and bilirubin $<2\times\text{ULN}$ without symptoms believed to be related to liver injury or hypersensitivity, and who can be monitored weekly for 2 weeks **OR**
- ALT $\geq 3\times\text{ULN}$ and $<5\times\text{ULN}$ (without elevated CPK, and/or myoglobin) and bilirubin $<2\times\text{ULN}$ without symptoms believed to be related to liver injury or hypersensitivity, and who can be monitored weekly for 4 weeks
- If ALT $\geq 5\times\text{ULN}$ and $<8\times\text{ULN}$ (without elevated CPK, and/or myoglobin) and **GGT is $\geq 1.5\times\text{ULN}$** to $< 3\times\text{ULN}$ without symptoms believed to be related to liver injury or hypersensitivity, and who can be monitored weekly for 2 weeks **OR**
- ALT $\geq 3\times\text{ULN}$ and $<5\times\text{ULN}$ (without elevated CPK, and/or myoglobin) and **GGT is $\geq 1.5\times\text{ULN}$** to $< 3\times\text{ULN}$ without symptoms believed to be related to liver injury or hypersensitivity, and who can be monitored weekly for 4 weeks

Required Actions

- Notify the Sponsor (Northwell Health) and GSK within 24 hours of learning of the abnormality to discuss subject safety.
- Subject can continue study treatment
- Subject must return weekly for repeat liver chemistries (ALT, AST, GGT, alkaline phosphatase, bilirubin) until they resolve, stabilize or return to within baseline
- If at any time subject meets the liver chemistry stopping criteria, proceed as described above for Required Actions and Follow up Assessments following ANY Liver Stopping Event
- If ALT decreases from ALT $\geq 5\times\text{ULN}$ and $<8\times\text{ULN}$ to $\geq 3\times\text{ULN}$ but $<5\times\text{ULN}$ (without elevated CPK, and/or myoglobin) and **GGT is $\geq 1.5\times\text{ULN}$** to $< 3\times\text{ULN}$, continue to monitor liver chemistries weekly.

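### Appendix C sets no repeat-testing interval or dosing decision when symptoms accompany a newly found ALT of 3 to <8xULN with normal CPK and myoglobin, GGT <3xULN, bilirubin <2xULN and INR not >1.5

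*Combined protocol and SAP*

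**What the plan says.** All rules cited here are in Appendix C unless another section is named.

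**Stopping criteria.** Dosing stops on an absolute ALT line (≥8xULN), an ALT-increase line (ALT bands 3 to <5 and 5 to <8xULN, persisting), a bilirubin line, an INR line, a cannot-monitor line and a symptomatic line. The symptomatic line covers ALT ≥3xULN without raised CPK and/or myoglobin, with GGT ≥3xULN, "associated with symptoms (new or worsening) believed to be related to liver injury or hypersensitivity".

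**Increased monitoring criteria with continued therapy.** Four criteria use the ALT bands: two add bilirubin <2xULN and two add GGT 1.5 to <3xULN. All four exclude raised CPK and/or myoglobin. The two for the upper band apply to patients "without symptoms believed to be related to liver injury or hypersensitivity, and who can be monitored weekly for 2 weeks"; the two for the lower band carry the same symptom condition with 4 weeks of monitoring. A further criterion concerns past IVIG: "For subjects who have had IVIG in the past, additional HBVDNA testing must be completed when ALT or AST elevations increase to" above 2.5xULN.

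**Required actions for the monitoring list.** "Notify the Sponsor (Northwell Health) and GSK within 24 hours of learning of the abnormality to discuss subject safety"; "Subject must return weekly for repeat liver chemistries", "until they resolve, stabilize or return to within baseline"; and study treatment may go on.

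**Stated rationale.** The criteria were "amended for this myositis protocol to accommodate for a specific population of myositis patients with ALT/AST abnormalities as a result of muscle injury".

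**The concern.** Symptoms that the investigator attributes to the liver or to hypersensitivity should bring closer follow-up of an ALT rise. Followed literally, these rules do the reverse in one region: adding symptoms takes the patient off the weekly-testing list without putting the patient on the stopping list.

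The symptoms are plausible with this drug. Study Drug Administration, item 4, names rash, nausea and fatigue among the delayed hypersensitivity symptoms seen with it, and the symptom note in Appendix C names the same three.

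At stake are how soon liver chemistries are repeated and whether the next infusion is given. In a multicentre trial, one site could take the symptom condition to imply stopping and another could fall back on the routine schedule. No endpoint or analysis is affected.

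**Working it through.** There is no plan figure to reproduce, so the check sets the rules side by side.

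**Conditions held fixed.** Bilirubin <2xULN; INR not >1.5 or not measured (otherwise the bilirubin or INR line stops dosing); CPK and myoglobin both normal; result newly found, so no persistence criterion is met yet; weekly monitoring possible.

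**Step 1: stopping lines for ALT 3 to <8xULN.** The absolute lines need ALT ≥8xULN. The ALT-increase, cannot-monitor and symptomatic lines each need GGT ≥3xULN. With GGT <3xULN, none applies.

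**Step 2: monitoring criteria.** All four ALT-band criteria require no symptoms. The two bilirubin-based ones have no GGT condition, so they take in every patient without symptoms here.

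**Step 3: count.** 2 ALT bands × 3 GGT bands × symptoms no/yes = 12 combinations. Both ALT bands give the same answer:

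| GGT (xULN) | No symptoms | Symptoms at first detection |
|---|---|---|
| <1.5 | monitoring list | neither list |
| 1.5 to <3 | monitoring list | neither list |
| ≥3 | monitoring list | stop |

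Without symptoms: 3 × 2 = 6 of 6 are listed. With symptoms: 1 × 2 = 2 stop and 2 × 2 = 4 are on neither list.

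**Step 4: time to the next panel.** Study Procedures and Schedule puts the metabolic panel and GGT at weeks 0, 2, 4, then every 4 weeks to week 64 (taking weeks 39-40 as week 40). That is 2 + (64 − 0)/4 = 18 intervals-and-endpoints counted as follows: weeks 0, 4, 8, … 64 give 17 time points, plus week 2, making 18. The gaps are 2 of 2 weeks and (64 − 4)/4 = 15 of 4 weeks.

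- On the monitoring list: first repeat after 1 week.
- On neither list: next routine panel after 2 weeks if found at week 0 or 2, and after 4 weeks if found from week 4 to week 60.

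Infusions follow the same weeks, so without a rule the next dose falls due at the visit where the next routine panel is drawn.

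**Step 5: does other text supply the missing rule?**

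- Adverse Events of Special Interest: abnormal liver enzymes are to be watched closely and reported to the sponsor at once. No interval or dosing decision.
- Note under the SAE definition: liver toxicities go to the Sponsor and GSK. No deadline for GSK outside the stopping criteria.
- SAE items g, h and i need GGT ≥3xULN, bilirubin ≥2xULN or INR >1.5. Item f rests on judgment.
- Study Drug Administration, item 2: a serious reaction ends administration. Milder or delayed symptoms are not covered.
- Closing note of Appendix C: investigator discretion applies only once a listed rule has been met.

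**The case against.** **The monitoring list is also a permission to keep dosing.** Its heading and required actions allow treatment to continue, so excluding symptomatic patients can be read as protective. This stands, and it rules out simply moving these patients onto the list. It does not supply the missing instruction.

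**Oversight exists.** Immediate sponsor reporting applies with no ALT, GGT or symptom threshold, and serious reactions end dosing. This stands. A reader might infer that these patients go unreported; the documents do not support that. The difference in notification is limited to the 24-hour deadline for GSK.

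**The rules were adapted for muscle-derived ALT.** True, but that reason does not reach patients whose CPK and myoglobin are both normal.

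**The past-IVIG criterion has no symptom condition.** It orders only hepatitis B DNA testing. If the required actions are read as applying to it, the gap is confined to patients without past IVIG.

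**Cases will be few.** This stands. The documents give no frequency, 30 patients are planned, and Adverse Events of Special Interest, item 6, reports no causal liver signal in the lupus studies. Many clinicians would probably retest early anyway.

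**Conclusion.** The gap is real but narrow: 4 of 12 rule combinations with normal CPK and myoglobin, under the conditions listed in the check. These are combinations of rules, not patients. What is missing is a repeat-chemistry interval, a GSK deadline and a decision on the next dose. It merits correction because the cost is small and the rules as written weaken specified follow-up when symptoms are present.

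Three stronger readings are not supported.

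- A reader might infer a far larger hole by adding raised CPK and myoglobin to the count: of 24 combinations, 16 are then on neither list. But 16 = 4 (this point) + 4 (raised CPK and myoglobin, GGT ≥3xULN) + 8 (raised CPK and myoglobin, GGT <3xULN). The 8 are best read as the intended exemption for muscle-derived ALT.
- A reader might infer that the group with raised CPK/myoglobin and GGT ≥3xULN is a second defect of equal weight. At ALT ≥8xULN that GGT level stops dosing "irrespective of CPK and/or myoglobin values", so the authors considered an override and chose where to set it. A lower threshold is an optional question for the Sponsor and GSK.
- A reader might infer that a patient already on weekly testing drops off when symptoms appear later. Weekly testing runs "until they resolve, stabilize or return to within baseline", so the point concerns only symptoms present at first detection.

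One limit: patients without symptoms, with normal CPK and myoglobin and GGT <3xULN, who cannot attend weekly are also on neither list. They are outside this point and the fix below does not cover them.

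**What to change.** Add one separate line to Appendix C for ALT 3 to <8xULN with normal CPK and myoglobin, GGT <3xULN, bilirubin <2xULN, INR not >1.5 or not measured, and symptoms attributed to liver injury or hypersensitivity when the rise is first found. It should require:

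- notice to the Sponsor and GSK within 24 hours;
- weekly liver chemistries until they resolve, stabilise or are back within baseline;
- the next dose withheld until the Sponsor and GSK decide whether to stop or continue.

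The existing permission to continue treatment should not apply to this line by default.

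The cost is one line of amendment wording, using tests already in the schedule. The downside is a few extra blood draws and possibly a delayed infusion in rare patients. At the same time the Sponsor and GSK could, if they wish, say whether raised CPK/myoglobin with GGT ≥3xULN at ALT 3 to <8xULN should have a monitoring interval.
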